### 7.3 LOST TO FOLLOW-UP

A participant will be considered lost to follow-up if he or she fails to return for 3 scheduled visits and study staff are unable to contact the participant after at least 3 attempts.

The following actions must be taken if a participant fails to return to the clinic for a required study visit:

- The site will attempt to contact the participant, reschedule the missed visit within 1 week, counsel the participant on the importance of maintaining the assigned visit schedule and ascertain if the participant wishes to and/or should continue in the study.
- Before a participant is deemed lost to follow-up, the investigator or designee will make every effort to regain contact with the participant (where possible, 3 text-messages and 2 telephone calls and, if necessary, a certified letter to the participant's last known mailing address or local equivalent methods). These contact attempts will be documented in the participant's medical record or study file.
- Should the participant continue to be unreachable, he or she will be considered to have withdrawn from the study with a primary reason of lost to follow-up.

## 8 STUDY ASSESSMENTS AND PROCEDURES

### 8.1 ENDPOINT AND OTHER NON-SAFETY ASSESSMENTS

The focus of this study is on the feasibility of carrying out the assessment of a primary tailoring variable (PTV). A PTV is the cutoff score to decide whether a participant showed a clinically meaningful response to BAT or BAT & mHealth at a 1-month follow-up point. The preliminary cutoff score for the pilot SMART is defined as a decrease in a PHQ-9 score from the "moderate" to "mild" (or below) depression symptom severity category after 4 weeks (or after 4 of 8 sessions of BAT). The rationale for the follow-up period is to identify early who is a "responder" or "non-responder" to a 1st-stage treatment. The "responder/non-responder" decision is used to decide whether, when, and how to adapt a 1st-stage treatment. The follow-up point is the mid-way point of the brief intervention, that is, after 3 of 5 BAT sessions are complete. This cutoff score is supported by a randomized placebo-controlled trial that showed BAT to be associated with reduced depression more per week than a cognitive therapy on a self-rating scale. The same depression rating is done at the final follow-up period at the end of the final intervention session.

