## 1 PROTOCOL SUMMARY

### 1.1 SYNOPSIS

Title:	Feasibility and acceptability of an adaptive treatment intervention for depression and engagement in HIV Care among Latinos living with HIV
Grant Number:	K01MH113475
Study Description:	This is the evaluation of the feasibility and acceptability of an adaptive intervention for depression and engagement in HIV care among Latinos living with HIV. The adaptive intervention is the sequencing of two low-risk behavioral interventions with text-messaging support. The focus of the study is on the sequencing of the interventions.
Objectives *:	Primary Objective: Feasibility of the intervention (i.e., execution of enrollment and intervention session completion rates). Secondary Objectives: Acceptability of the intervention (i.e., evaluation of engagement with intervention). Full details listed in the protocol.
Endpoints *:	Primary Endpoint: Half-way through active engagement with intervention (4 of 8 sessions completed) - this is the follow-up period dictating the sequencing decision. Secondary Endpoints: 12 weeks after enrollment - this is the final follow-up period.
Study Population:	A total of 45 Latino(a)/ Hispanic adult patients (18 or older) that are English or Spanish speaking, are living with HIV, report a mild level of depressive symptoms, and receive care at San Francisco General Hospital Ward 86.
Phase or Stage:	Not applicable
Description of Sites/Facilities Enrolling Participants:	Participants are recruited from Ward 86, at Zuckerberg San Francisco General Hospital in San Francisco, CA. This is a clinic setting with exam rooms, waiting room, and office space. Mission Hall is a research building at the Mission Bay Campus at U.C. San Francisco and includes private office and research study space.
Description of Study Intervention/Experimental Manipulation:	The interventions are behavioral activation therapy (BAT), cognitive-behavioral therapy (CBT) and text-messaging support. BAT is a 8-session one-on-one, in-person or video conferencing, intervention. CBT is an 11-session, one-on-one, in-person or video conferencing, intervention. Text-messaging support are one- and two-way SMS messages.
Study Duration *:	We expect a total of 12-months are needed to enroll 45 participants.
Participant Duration:	Participants are expected to be followed for 3 months.

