## 5 STUDY POPULATION

### 5.1 INCLUSION CRITERIA

Inclusion criteria include:

- HIV positive
- 18 years of age and older
- Self identifies as Latino/Hispanic
- Speak English or Spanish
- Receives HIV care at Ward 86
- Screened in with at least mild depression severity score to start (Patient Health Questionnaire-9 score >3; PHQ)
- Agrees to discuss depression, treatment preferences, and mobile health
- Owns a mobile phone that can send/receive short-message service (SMS) text messages
- Agrees to participate in the intervention that lasts three months
- Agrees to have medical and clinical data abstracted
- Able and willing to consent to participate

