### 5.2 EXCLUSION CRITERIA

Exclusion criteria include:

- Not HIV positive
- Under 18 years of age
- Screened as having normal (PHQ-9 score of <2) or severe depression rating score (PHQ-9 score of 20 or higher).
- Does not self-identify as Latino/Hispanic
- Does not speak English or Spanish
- Does not receive HIV care at Ward 86
- Does not agree to discuss depression, treatment preferences, and mobile health
- Does not own a mobile phone that can send/receive short-message service (SMS) text messages
- Does not agree to participate in the intervention that lasts three months
- Does not agree to have medical and clinical data abstracted one year after baseline
- Not able and willing to consent to participate

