3. **Cognitive therapy** attempts to improve a person's depressed mood by teaching them that how a person feels and behaves is a function of how they think about themselves and the world around them. The key feature of depression in cognitive theory is negative thinking. To remedy negative thinking requires specific skills to learn how to monitor one's thoughts, and then to use strategies to think more adaptively to counteract the negative thinking. In cognitive therapy, by changing thoughts you change behavior and emotions. Cognitive theory requires more time and is a higher-order approach, which is why all participants are not starting with it. The cognitive component in "cognitive-behavioral" therapy typically comes later on in the program after the behavioral component has been learned. For this reason, we are only randomizing participants to receive this more time-intense program if the behavioral therapy is not sufficient to change depression ratings.

Participants in this study will be HIV+ Latino/as receiving care at the Ward 86 Salud or Women's Clinic, a Latino-serving HIV clinic at ZSFG. The SMART trial has three components: 1) brief, Behavioral Activation Therapy (BAT) 2) cognitive-behavioral therapy (CBT), and a text-messaging tool (mHealth).

- Delivery Method-Texts and interventions sessions will be completed either in person or via secure video chat platforms hosted by UCSF (i.e., HIPAA-compliant Zoom Video Conference platform). All text-messages are sent on secured encrypted UCSF Apple iPhones and with text-message platforms, such as Signal or Mosio.
- Session Length- Each session will ideally last 50-60 minutes.

- **Intro Session-** The study counselor will meet with the participant individually to complete a brief assessment and to identify topics to address during the counseling sessions. The counselor and the participant will discuss pressing issues, ongoing concerns, and areas identified as priorities by the participant.

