Conversely, participants randomized to the (A2) BAT & text-message support will receive an identical BAT program with the addition of one and two-way personalized text messages that will be delivered twice a week to facilitate engagement with the intervention activities.

**Text-Messages** - One-way messages will be sent as appointment and BAT adherence reminders (e.g., "Please remember to fill out your social activity planner?", while two-way text messages will be sent as "check-ins" with participants in the form of a mobile interventionist (e.g., "How is your activity planning going? If you need assistance, I can remind you of what activities you said you could do"). Participants will be asked to respond to these two way-text messages at their earliest convenience.

After three sessions of the five planned sessions have been completed, an assessment of the participants depression will be made using a cutoff score on the Patient Health Questionnaire-9 (PHQ-9), a self-reported rating scale for depression (this is called a "primary tailoring variable"). This primary tailoring variable will dictate the second sequence. Based on their PHQ-9 score, participants are coded as a "responder" or "non-responder;" a code that dictates whether their initial randomization assignment is 1) maintained, 2) augmented, or 3) switched to a second component (this is the second randomization and "adaptive" component).

**Participants who were randomized to BAT alone and were coded as "non-responders" will be randomized to:** 1. additionally receive text-message support, or 2. switched to receive CBT & text-message support. If switched to CBT & text-message support, participants will complete a total of eight intervention sessions that can be re-arranged to fit patient needs. CBT sessions will be scheduled once a week for 60 minutes (as described above, CBT integrates cognitive theory principles with behavioral theory principles, and thus, is more intensive). If participants randomized to BAT alone during their first stage of treatment and responded, they continue with maintenance of their BAT sessions.

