#### 6.1.2 ADMINISTRATION AND/OR DOSING

We are taking a brief behavioral intervention for depression, a text-message support intervention, and a cognitive-behavioral intervention, and sequencing how each is rolled out based on how participants respond. In a traditional approach, we would be comparing each component individually as standalone interventions compared to a control condition, and evaluating their effects. In a SMART, you start with the lowest burden/low dose intervention, and only increase as needed. This study is solely focused on feasibility and acceptability.

There are situations where multiple treatments are known to be effective, but what is unknown is whether every person benefits the same from all of them. In the depression field, we do not know how best to package what are considered efficacious interventions - 1) behavioral activation therapy, 2) cognitive-behavioral therapy, and 3) text-message support to treat depression and promote adherence to medication and clinic appointments. We will use a SMART design to evaluate if it is feasible and acceptable to sequence these behavioral interventions for depression.

**STARTING POINT:** Patients are recruited and then randomized to one of two active arms. The first randomization is to one of two interventions (A1 and A2). Both A1 and A2 are an already-established efficacious brief behavioral intervention, the only difference is that one will include a text-message support intervention (A1 versus A2 + Text-message support), which is the experimental factor we are testing, i.e., whether text-message support is the key factor between A1 and A2. At baseline, where participants are randomized, we will measure their depression using a standard rating scale.

**FIRST OPTION:** All participants will complete 4 of 8 sessions of A1 or A2, at which point we will make another depression assessment. This assessment will indicate if participants responded well to this first "assignment" (i.e., improved depression ratings) or did not respond well (i.e., no change in depression ratings or worse depression ratings). If they respond well, nothing changes and they proceed as normal through the 5-session program. If they do not respond, i.e., show no improvement or show worse ratings, we "adapt" the intervention because we have evidence that the intervention is not currently relieving depressive symptoms.

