## 6.5 CONCOMITANT THERAPY

All participants will be able to receive pharmacotherapy, other psychotherapy, case management and social work services during the study, as this does not affect their eligibility and reflects the real-world circumstances of patients who may benefit from our study in the future. The implementation of the pilot SMART at ZSFG will integrate an adaptive intervention into an HIV care site, and use Spanish and English text-messages to promote adherence to the intervention. Importantly, this study will not interfere in any way with the standard of HIV primary care regularly received by patients at the ZSFG Ward 86 Clinic. Participants in a SMART are randomized to an evidence-based treatment intervention for depression, with the only differentiating factor being the use of text-messaging to support

adherence to the intervention's protocol. It is only when a patient does not respond to their assigned treatment do we investigate the next course of action in the form of a second-stage treatment, which is adapted to their particular case. Furthermore, no other services for depression, including pharmacotherapy, will be denied. For each patient, we are writing a formal letter to their HIV care provider to let them know that their patient is in this study because they reported mild to moderate depression severity and to continue to prescribe any treatment they deem appropriate. **All together, we believe that our study design, and feature of not withholding any treatment, does not place any participant at greater risk than what they would encounter with any other services available for their depression.**

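### Section 8.1's responder rule does not fit participants who start mild, and section 6.1.2 states a different rule, so the same participant can be coded either way

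*Combined protocol and SAP*

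**What the plan says.** Section 8.1 gives the only specific PHQ-9 responder rule in the visible text: a "decrease in a PHQ-9 score from the 'moderate' to 'mild' (or below) depression symptom severity category", assessed part-way through behavioural activation therapy (BAT). The section labels this cutoff preliminary.

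The population is wider than that rule. The synopsis describes participants who "report a mild level of depressive symptoms". Section 5.1 requires "Screened in with at least mild depression severity score to start (Patient Health Questionnaire-9 score >3; PHQ", and section 5.2 excludes anyone "Screened as having normal (PHQ-9 score of <2) or severe depression rating score (PHQ-9 score of 20 or higher". The letter to providers in section 6.5 will say that "their patient is in this study because they reported mild to moderate depression severity".

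Section 6.1.1 says that "an assessment of the participants depression will be made using a cutoff score on the Patient Health Questionnaire-9 (PHQ-9" and that the resulting code determines what happens next. Non-responders in either arm are re-randomised, and one option in each arm is a switch to CBT with text messages. The same section says the study is "only randomizing participants to receive this more time-intense program if the behavioral therapy is not sufficient to change depression ratings".

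Section 6.1.2 describes response in other terms. Participants whose ratings improve keep their first treatment. Those who "did not respond well (i.e., no change in depression ratings or worse depression ratings" are eligible for re-randomisation.

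**The concern.** The responder code is the decision point of a SMART. It determines who is randomised a second time, who may be moved to a longer therapy, and which of the six outcome groups each person joins. Section 8.1 describes a move that only a moderate starter can make, although mild starters are an intended part of the sample. Section 6.1.2 covers every starting score but does not agree with 8.1. Two staff members could each follow the protocol and code the same person differently.

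Section 8.1 says the study's focus is whether this tailoring variable can feasibly be assessed, and section 9.4.1 judges retention within each outcome group. An unclear code therefore affects what the pilot is meant to learn, even though no efficacy hypothesis depends on it.

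**Working it through.** **Eligible scores.** Section 5.1 requires PHQ-9 above 3, so the lowest eligible score is 4. Section 5.2 excludes 20 or higher, so the highest is 19. The documents give no mild/moderate cut-point and name no category between moderate and severe. I therefore treat 4 to 19 as mild or moderate.

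**The rules side by side** (R = responder, NR = non-responder):

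| Participant at the decision point | 8.1, literal move from moderate | 8.1, read as mild or below at follow-up | 6.1.2, any improvement |
|---|---|---|---|
| Starts mild, improves | NR | R | R |
| Starts mild, unchanged | NR | R | NR |
| Starts mild, worsens to moderate | NR | NR | NR |
| Starts moderate, falls to mild or below | R | R | R |
| Starts moderate, improves but stays moderate | NR | NR | R |
| Starts moderate, unchanged or worse | NR | NR | NR |

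Three of the six rows depend on which text is followed. Two of those three concern mild starters.

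**The plan's own figure.** Section 9.2 uses six groups, at least 4 per group, 80% probability, 50-60% non-response and 10% attrition, and arrives at 45. I assume equal first-stage arms of n completers, non-responders X ~ Binomial(n, p), and a balanced second-stage split. An arm succeeds if n - X >= 4 and floor(X/2) >= 4; the two arms' probabilities are multiplied. The smallest total reaching 0.80 is:

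- p = 0.50: 42 (0.818); 42/0.9 = 46.7, so 47
- p = 0.55: 38 (0.819); 38/0.9 = 42.2, so 43
- p = 0.60: 36 (0.827); 36/0.9 = 40

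The stated 45 lies within 40-47. An unbalanced (simple random) second split would need 53-64, which does not match, so I keep the balanced model.

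**What each reading of 8.1 does to non-response (illustrative).** Let m be the share starting mild, q the non-response rate among moderate starters (0.50 or 0.60, borrowed from 9.2), and w the share of mild starters who are moderate at follow-up.

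- Literal reading: p = m + (1 - m)q
- Mild-or-below reading: p = (1 - m)q + m·w

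Completers: 45 × 0.9 = 40.5, taken as 40, or 20 per arm. An arm then succeeds when X is 8 to 16.

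| Case | p at q = 0.50 / 0.60 | P(all six groups >= 4) |
|---|---|---|
| No mild starters | 0.50 / 0.60 | 0.752 / 0.927 |
| m = 0.2, literal | 0.60 / 0.68 | 0.927 / 0.848 |
| m = 0.2, mild or below, w = 0 | 0.40 / 0.48 | 0.341 / 0.681 |
| m = 0.2, mild or below, w = 0.2 | 0.44 / 0.52 | 0.516 / 0.812 |
| m = 0.5, literal | 0.75 / 0.80 | 0.600 / 0.346 |

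The literal reading raises overall non-response. In the cases shown, the other reading lowers it. The rate under 6.1.2's rule cannot be derived from the documents.

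**The case against.** The strongest reply is that 8.1 should not be read alone. Section 6.1.2 is the administration section, covers every baseline score, and says that improvers stay on their first treatment. Section 6.1.1 reserves CBT for people whose ratings BAT does not change. On this view 8.1 only describes the typical moderate case, and staff would not re-randomise an improving mild starter.

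This defeats one tempting reading. A reader might infer from 8.1 that the protocol directs improving mild starters to be re-randomised. Taken as a whole it does not, because 6.1.2 says the opposite. The conflict remains, however. Section 8.1 holds the only stated cutoff, 6.1.1 says a PHQ-9 cutoff makes the code, and 6.1.2 itself refers to a cutoff score. Nothing says which section governs.

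A reader might also set 9.2 against 8.1: the planning rate is quoted for people with mild depression, implying that 40-50% of them respond, while the literal rule allows none. That contrast is unsafe. Section 9.2 adds that results were similar at higher severity, and its criterion is a 50% reduction at 4 months, not a category change at about 4 weeks.

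It is also fair to say that 8.1 may ask more of moderate starters than any improvement at all. The difficulty in that row is the disagreement with 6.1.2, not the strictness of the threshold.

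Finally, the stakes are limited, and this stands. The cutoff is preliminary, there are no hypotheses, every arm receives active therapy, and no other care is withheld.

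**Conclusion.** The point holds as a conflict between sections, together with a gap in 8.1 for mild starters. No reading of 8.1 classifies mild starters consistently with 6.1.2, and moderate starters who improve within their category are also coded differently by the two sections. This should be fixed, but it does not threaten the trial.

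Its size cannot be stated, because the documents do not give the expected share starting mild. The probabilities above also rest on 40 completers, a balanced second split, and 9.2's rate applied to a different criterion and time point. They show that the choice of reading matters, not that a particular shortfall will occur. A reader might infer that 45 is too few. The figures do not support that: 45 is reproduced under the plan's inputs, the literal reading with 20% mild stays above 0.80, and the 0.752 at 50% non-response arises with no mild starters at all.

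The SMART figure was not available. If it contains a cutoff, the texts of 8.1 and 6.1.2 would still need to agree.

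**What to change.** In 8.1, state one responder rule based on change from the participant's own baseline PHQ-9, so that every eligible score from 4 to 19 gets one code. Give any cut-points it uses, and have 6.1.1 and 6.1.2 refer to it. The clinical choice is the sponsor's.

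A 50% reduction would match the criterion behind the 9.2 rate and works across the range: a starter at 4 needs a score of 2 or less, and a starter at 19 needs 9 or less (half of 19 is 9.5). A fixed point reduction also works if it is no larger than 4; otherwise the lowest starters again cannot respond.

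Then confirm that 50-60% non-response is plausible under the chosen rule at the decision point. If it is not, keep 45 and restate the 80% probability.

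Section 5.5 describes recruitment changes after March 2020, so some participants may already be coded. Let those codes stand, record which rule was used, and report this with the group counts.

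The cost is a wording amendment, which needs IRB approval before use. Depression ratings are already scheduled at every visit, so no visit, measure or participant is added.

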## 8.2 SAFETY ASSESSMENTS

Not applicable as this intervention does not involve any medical or pharmacological components that would warrant a physical safety assessment.

## 8.3 ADVERSE EVENTS AND SERIOUS ADVERSE EVENTS

### 8.3.1 DEFINITION OF ADVERSE EVENTS

The definition of adverse events followed is from the U.S. Department of Health and Human Services Office for Human Research Protections. An adverse event is defined as any undesirable experience associated with the engagement with any aspect of the study activities. While the risks of any adverse events are deemed to be extremely rare, we will follow the guidance in the following sections.

